8.4. Unblinding

In the event of emergency, the site Investigator may require that the blind be broken for the subject experiencing the emergency when knowledge of the subject's treatment assignment may influence the subject's clinical care. Emergency unblinding can occur by contacting Emmes during business hours or by contacting the unblinded vaccine formulation expert after business hours. Every effort will be made not to unblind the subject unless it is considered necessary for the welfare of the subject. Prior to unblinding, the site Investigator is encouraged (to the extent possible, without jeopardizing the subject's health) to contact the Sponsor (or designee) to discuss the decision to break the blind. The site PI will be expected to provide a rationale for the necessity of unblinding based on the expectation that knowledge of the subject's treatment assignment will have a meaningful impact on the subject's medical care in the short term. If a subject's treatment assignment is unblinded, the subject will remain in the study and continue with protocol-defined study visits, but not receive further vaccinations. The decision to unblind will be communicated to any regulatory bodies (e.g., institutional review boards [IRBs]) as required. At the end of the study, documentation of all unblinded subjects (and the rationale for unblinding) will be incorporated into the Trial Master File.

8.5. Vaccination

After initial screening and informed consent, eligible volunteers will be vaccinated with *S. flexneri* 2a Invaplex_{AR}-DETOX Lot 1972 or placebo (saline). The vaccine will be administered IM on Days 1, 22, and 43. The investigational product administration procedure is outlined in detail in the Manual of Procedures (MOP). Briefly, the IM vaccination site (deltoid muscle) will be pre-treated with an alcohol pad and the vaccine will be administered using a 1-inch needle. Approximately 100 µL of appropriately formulated vaccine product or placebo will be administered. Subjects will be observed for at least 30 minutes post-vaccination and given symptom diaries to record local and systemic reactions for 7 days post vaccination for each dose. After the 30-minute observation period, an assessment will be performed including vital signs and the recording of all adverse events. Subjects will return approximately 24 hours after vaccination for a follow-up examination. For each subsequent immunization, the injection will be given in alternate deltoid regions from the previous vaccination. An exception may be needed if there is pain/tenderness, erythema, edema, pruritus, induration, or rash at the planned site of vaccination. In this case, the Principal Investigator, following discussion with the Independent Research Monitor, may exercise the discretion to administer the vaccination on the same arm as the previous vaccination. The site of vaccine administration will be recorded in the source documents.

8.5.1. Vaccination Follow-Up

The timing and number of follow-up visits are delineated in the Time and Events Schedule (Table 8) and are scheduled to coincide with vaccination or specimen collection visits. These visits may include a brief history, targeted exam, blood, stool, and salivary specimen collection, and a reminder to the volunteer to contact the investigator if s/he experiences any medical problems. Subjects will return approximately 24 hours and 7 days after vaccination for follow-up.

Approximately 6 months from final vaccination all subjects will be contacted via telephone to assess for a final safety assessment. A history for any additional serious new diagnoses or hospitalizations will be solicited. Three attempts will be made and documented; after 3 unsuccessful attempts a certified letter and/or email will be used to request the subject to contact the study team.

8.6. Endpoints

8.6.1. Safety

Safety monitoring will be undertaken using in-person symptom surveillance, symptom diaries, and targeted physical exams. Solicited adverse event monitoring will survey and specifically inquire about symptoms listed in section 11.6.2. Abnormalities will be described in detail in order to monitor progress. This will include the name of the adverse event, the date and time of onset and offset (duration), severity, and Principal Investigator determination of relationship to the investigational vaccine. Safety monitoring labs will also be performed on Days 8, 29, and 50. Clinical outcomes will be prospectively defined and actively surveyed during the study. The study procedures are detailed in Table 8.

Clinical definitions will be used to grade the severity of symptoms in accordance to the severity scale included in section 11.8.3.

8.6.2. Immunology

A secondary objective is to assess IgG and IgA serologic and Antibody in Lymphocyte Supernatant (ALS) responses to *S. flexneri* 2a Invaplex using methods previously established. Seroconversion will be defined as a \geq 4-fold increase in endpoint titer between pre- and post-vaccination samples. Peripheral Blood Mononuclear Cells (PBMCs) will be collected to determine antigen-specific IgG and IgA titers in ALS samples. An ALS response is defined as \geq 4-fold increase in antibody titer at any point post-vaccination as compared to baseline titers. For serologic and ALS assays, high-titer specimens will be included on each plate to track day-to-day interassay variation. For each antigen, pre- and post-vaccination serum samples will be assayed side-by-side. The antibody titer assigned to each sample will represent the geometric mean of duplicate tests. Reciprocal endpoint titers less than the starting dilution of the assay will be assigned a value of half the starting dilution for computational purposes.

Secondary immunologic evaluations (an exploratory objective) may include serologic and ALS responses to additional antigens (*S. flexneri* 2a LPS, IpaB, IpaC), additional IgG subclasses, IgM responses, and serum bactericidal antibody (SBA) titers against *S. flexneri* 2a 2457T (responders defined as \geq 9-fold increase in SBA titer at any point post-vaccination compared to baseline titers). Stool samples will be collected to assess antigen-specific fecal Ig responses. A fecal response will be defined as a \geq 4-fold increase from baseline.

Samples will also be collected, processed, and archived for potential future analysis as follows. PBMCs will be collected for antigen-specific memory B/T cell analyses, antibody secreting cell (ASC) assay, and $\alpha 4\beta 7^+$ B cells. Concurrently, saliva samples may be collected to assess mucosal IgA and IgG antibody responses. CRP responses in serum after initial vaccination will be collected for exploratory correlation with immune responses and AEs.

8.7. Investigational product

8.7.1. Invaplex_{AR}-DETOX

S. flexneri 2a Invaplex_{AR}-DETOX Lot 1972 was produced under cGMP at the WRAIR Pilot Bioproduction Facility, [name]. The individual components IpaB (Lot 1757), IpaC (Lot 1771) and detoxified LPS (Lot 1902) were assembled into the Invaplex_{AR}-DETOX complex and subsequently purified by ion-exchange chromatography yielding the bulk drug product (Lot 1954). The drug product, designated as Lot 1972, was filled in 2mL glass vials, stoppered and sealed, and stored at $-80 \pm 10^\circ\text{C}$.

Figure 3: Label from a vial of Invaplex_{AR}-DETOX, Lot 1972

Shigella flexneri 2a WR30 Artificial
 Invaplex (Invaplex_{AR}-Detox)
 BPR No.: BPR-1214-00 Lot No.: 1972
 Contents: 0.6 ml \pm 0.06 Storage: $-80 \pm 10^\circ\text{C}$
 Caution: New Drug - Limited by Federal (or United States) law to investigational use.
 Date of Mfg.: 15 Jan 16
 Manufactured By: WRAIR, [name] 20910

8.7.2. Investigational Product Preparation

On the day of vaccination, the product will be used to formulate the appropriate vaccine preparations for the clinical groups. The vaccine will be used within 6 hours of preparation. Prepared vaccine or open vials will not be saved for use on another study day. Any remaining vaccine product will be properly disposed of in accordance with the MOP. Vaccine formulation for each of the groups is described in detail in the MOP.

8.7.3. Investigational Product Accountability

The sponsor is responsible for authorizing the release for distribution of the investigational products to the study site. The NMRC Enteric Diseases Department and/or WRAIR will arrange for shipment, under appropriate conditions, of the investigational products to the clinical site. At the WRAIR CTC, investigational product inventory logs will be maintained in the accountability files. The Release for Use Memo signed by the sponsor's representative gives permission to the WRAIR Pilot Bioproduction Facility to release product to the PI. After the investigational product is distributed, the PI is responsible for and will maintain logs of investigational product receipt, storage, reconstitution, accountability by subject, and investigational product remaining before final disposition. These logs will be maintained in the regulatory files at the WRAIR CTC. The PI may delegate, in writing, this responsibility to another individual, but the PI is ultimately responsible for the investigational product and its proper storage upon receipt at the study site until it is transferred back to the sponsor or designee, utilized as directed by the sponsor or destroyed. Any excess formulated vaccine remaining from vaccination day will be disposed of or used for research purposes as authorized by the sponsor. All used or partially used investigational product and empty vials will be destroyed or used for nonclinical research purposes as per the MOP.

8.8. Duration of Subject Participation

Screening of volunteers will occur during a period of up to 60 days prior to initial vaccinations. Subjects will receive 3 vaccinations on Days 1, 22, and 43. Clinical follow-up will occur as delineated in the Time and Events schedule (Table 8). A phone survey will occur at approximately 6 months after the final vaccine dose. This phone survey will specifically inquire if the subject has experienced any new serious health problems or hospitalizations since their last study follow-up. Inclusion criteria require that a subject be available for the required follow-up period and scheduled clinic visits. Therefore, no military subjects will be enrolled in the study if a known deployment is to conflict with his or her involvement. If there is an unexpected deployment, efforts (e.g., telephone, e-mail, command mail) will be undertaken to obtain safety follow-up data per the protocol schedule.

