8.12.1.3. Pregnancy

During initial screening and prior to each vaccination, a urine pregnancy test will be performed. Subjects with a positive test will be excluded from the study. A final urine pregnancy test will be conducted during the last clinic visit. Female subjects of childbearing potential must agree to use an effective method of birth control (birth control pills, injection hormonal contraceptive, implant hormonal contraceptive, hormonal patch, IUD, sterilization by hysterectomy or tubal ligation, spermicidal products and barrier methods such as cervical sponge, diaphragm, or condom) during the study and 3 months following the last vaccination. Abstinence is acceptable. While female subjects will not be required to disclose their method of birth control, they will be counseled during the initial screening on acceptable forms of birth control required for study enrollment. At each visit, female subjects will be reminded that they must agree to use effective

contraception to remain in the study. Female subjects should not become pregnant during the study and for at least 3 months after the last vaccine dose.

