11.5.4.7. Pregnancy Screen

A urine sample for pregnancy testing (female subjects of childbearing capacity) will be collected at the screening visit. Pregnancy tests will also be obtained on each day of vaccination and at the final in-clinic study visit. A positive pregnancy test prior to vaccination will result in no additional study vaccinations being provided. Any subjects who become pregnant during the study will be removed from receiving further treatment with Invaplex_{AR}-DETOX and followed until the end of their pregnancy. Procedures to be followed in the event a study participant becomes pregnant during the study period are outlined in 11.9.2.1.

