11.9.2. Reporting Additional Immediately Reportable Events to the Sponsor and the NMRC IRB

11.9.2.1. Pregnancy

Each pregnancy must be reported *immediately* (within 72 hours of identification) by e-mail or fax to the sponsor and the NMRC IRB.

Subjects who become pregnant after receiving the first dose of vaccine or up to 3 months after the last vaccination will be followed to term, and information will be gathered for outcome, date of delivery, and health status of the mother and child including the child's gender, length, and weight. Complications and/or abnormalities should be reported including any premature terminations. A pregnancy is reported as an AE or SAE only when there is suspicion that the investigational product may have interfered with the effectiveness of contraception or there was a serious complication in the pregnancy including a spontaneous abortion or an elective termination for medical rationale. Principal investigator will notify study monitor, the local IRB, the research monitor and the sponsor for subjects that become pregnant during the study. The subject will be asked to provide serial follow-ups on the status of her pregnancy as well as provide health information on her infant following delivery. The subject will be asked to provide copies of clinic visits only if needed. The Subjects will receive no further vaccinations but will continue safety monitoring and all follow up visits as noted in the study schedule.

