8.5. Pregnancies

For any subjects in the Safety population who become pregnant during the study, every attempt will be made to follow them through completion of pregnancy to document the outcome, including information regarding any complications with pregnancy and/or delivery. Listings of pregnancies and outcomes will be presented ([Listing 15, Appendix C](#)).

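### Pregnancies up to 3 months after the last dose must be followed to term, but the last 62 or so of those days (about 47% of the window from first dose) have no scheduled pregnancy test or question

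*Protocol*

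**What the plan says.** **The obligation.** Protocol 11.9.2.1 states: "Subjects who become pregnant after receiving the first dose of vaccine or up to 3 months after the last vaccination will be followed to term". Outcome, delivery date and infant health are to be collected, and each pregnancy is to be reported to the sponsor and the IRB within 72 hours of being identified. Protocol 8.12.1.3 uses the same horizon: "Female subjects should not become pregnant during the study and for at least 3 months after the last vaccine dose".

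**The tests.** Protocol 11.5.4.7, after the screening test: "Pregnancy tests will also be obtained on each day of vaccination and at the final in-clinic study visit". Protocol 8.12.1.3 agrees: "A final urine pregnancy test will be conducted during the last clinic visit". The final clinic visit is Day 71.

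**The later contact.** One contact is scheduled after Day 71, the Day 223 telephone call. Its content is described in several places:
- Protocol 8.8: "This phone survey will specifically inquire if the subject has experienced any new serious health problems or hospitalizations since their last study follow-up"
- Protocol 8.5.1, which calls it a final safety assessment: "A history for any additional serious new diagnoses or hospitalizations will be solicited"
- Protocol 11.8.1: new-onset SAEs.
- Protocol synopsis, study design: adverse events, with no limit to serious ones. SAP Table 18 is consistent with this, since it has rows for any AE between Visit 11 and Visit 12.

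**The SAP.** Section 8.5 promises follow-up and a listing (Listing 15), introduced by "For any subjects in the Safety population who become pregnant during the study". It does not say how pregnancies are to be found.

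**The concern.** The protocol sets a follow-up duty that runs well past its last pregnancy test, and no later scheduled step asks about pregnancy. Protocol 11.9.2.1 treats a pregnancy as an AE or SAE only in stated circumstances: suspected interference with contraception, or a serious complication. A woman with a normal ongoing pregnancy at the Day 223 call could therefore answer every specified question truthfully and report nothing.

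This vaccine has not been given to humans before, and safety is the primary objective. If no one asks, an empty pregnancy listing could mean that no exposed pregnancy occurred, or that none was reported. Birth outcomes are also at risk. A congenital anomaly is an SAE under protocol 11.6.3, but for conceptions in this interval delivery would normally come after the last scheduled contact.

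**Working it through.** **Inputs.** Protocol 8.8: "Subjects will receive 3 vaccinations on Days 1, 22, and 43". Last test at Day 71 and call at Day 223 (protocol Table 8). Windows: dose 3 ±2 days, Day 71 ±4 days, Day 223 ±28 days (protocol Table 8; SAP 4.4.8 for the dose).

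**The plan's own figures.** SAP Table 2 gives post-dose days of 28 for Day 71 and 180 for Day 223. Both reproduce: 71 − 43 = 28 and 223 − 43 = 180. The plan thus counts 6 months as 180 days, so 3 months is taken as 90 days.

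**Length of the window.** End = 43 + 90 = Day 133. Length from first dose = 133 − 1 = 132 days.

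**Part after the last test.** 133 − 71 = 62 days.
- Share of the whole 11.9.2.1 window: 62/132 = 47.0%.
- Share of the 3 months after the last dose: 62/90 = 68.9%.

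**Sensitivity.**

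| Case | Days after last test | Share from first dose | Share of post-dose-3 period |
|---|---|---|---|
| 3 months = 90 days | 62 | 62/132 = 47.0% | 62/90 = 68.9% |
| 3 months = 91 days | 63 | 63/133 = 47.4% | 63/91 = 69.2% |
| 3 months = 92 days | 64 | 64/134 = 47.8% | 64/92 = 69.6% |
| Dose 3 at Day 41, visit at Day 75 (90 days) | 56 | 56/130 = 43.1% | 56/90 = 62.2% |
| Dose 3 at Day 45, visit at Day 67 (90 days) | 68 | 68/134 = 50.7% | 68/90 = 75.6% |

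No allowance is made for conceptions too recent for the Day 71 test to detect. Any such allowance would lengthen the gap.

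**Could the call close the gap?** The call falls between 223 − 28 = Day 195 and 223 + 28 = Day 251. That is 62 to 118 days after Day 133. For conceptions between Day 71 and Day 133, it comes 195 − 133 = 62 to 251 − 71 = 180 days after conception. One direct question could therefore cover the whole interval in retrospect, for every woman who is reached.

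**Birth outcomes.** Assuming about 266 days from conception to term (not in the documents), delivery would fall between 71 + 266 = Day 337 and 133 + 266 = Day 399. Both are later than the latest permitted call at Day 251.

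**Expected numbers.** The documents give neither a sex split nor a pregnancy rate. Assume 30 of the 60 subjects are women of childbearing capacity, with a pregnancy rate of 1% to 10% a year. Then 30 × 62/365 = 5.1 woman-years, or about 0.05 to 0.5 expected pregnancies in the gap.

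**The case against.** The strongest case on the other side has five parts.

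1. **The call is broader than protocol 8.8 alone suggests.** The synopsis speaks of adverse events, and SAP Table 18 expects AE counts after Visit 11. This stands as a description of the call. It does not close the gap, because 11.9.2.1 does not make an uncomplicated pregnancy an AE either.

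2. **Complications would be caught.** A reader might infer that miscarriages would be missing from the SAE count. The documents do not support that. Protocol 11.6.3 lists abortion and stillbirth as SAEs, 11.9.2.1 counts spontaneous abortion as a serious complication, and 11.8.1 has the call assess new SAEs. A miscarriage before the call is within what is asked. What remains uncovered is the ongoing normal pregnancy and any birth outcome after the call. Protocol 11.8.2 adds that a related SAE brought to the investigator's attention after the study is still reportable, but investigators need not seek such events.

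3. **Women may report pregnancies themselves.** A reader might infer that the 11.9.2.1 rule cannot be carried out at all. That goes too far. Reporting is triggered by identification from any source, and women are counselled at screening and reminded at each visit about contraception. The consent form and the Manual of Procedures were not available for this review, and either could hold a self-report instruction or a pregnancy prompt. The supportable statement is that the protocol and SAP schedule no active ascertainment.

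4. **The numbers are small.** The 47% is a share of calendar days, not of pregnancies. Well under one pregnancy is expected in the gap on the assumptions above, and one subject in five receives placebo. This stands, and it limits the weight of the point.

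5. **The SAP wording may already be wide enough.** A reader might infer that SAP 8.5 excludes these pregnancies. That is not established. SAP 6.2 runs the final analysis through Day 223, and Day 223 is Visit 12 in SAP Table 2. Yet Table 8 of the protocol labels that contact post-study, and protocol 8.12.1.3 names the study and the 3 months after the last dose separately. The phrase is ambiguous and needs clarifying. Replacing it with the 3-month window alone could drop conceptions between Day 133 and Day 223 that it may now cover.

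**Conclusion.** The point holds as a gap between the protocol's pregnancy rule and its schedule. About 62 of 132 days (47%; 43% to 51% across the permitted visit and dose windows) have no scheduled active ascertainment. Measured against the 3 months after the last dose alone, the share is about 69% (62% to 76%). The denominator should be stated whenever either figure is used.

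This rests on three things: 3 months counted as 90 days, which follows the plan's own day count; the call asking what the protocol specifies and no more; and no pregnancy prompt in the documents not seen. Uncomplicated pregnancies conceived after Day 71, and birth outcomes after the call, would then be known only through spontaneous report. An empty pregnancy listing would not show that no exposed pregnancy occurred.

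No primary or secondary result is affected. The change is still worth making, because it lets the protocol meet its own safety rule at almost no cost.

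**What to change.** **Protocol 8.5.1, 8.8 and 11.8.1.** For women of childbearing capacity, add to the Day 223 call a question on any pregnancy since the last visit, with the estimated conception date. Handle those conceived within the 11.9.2.1 window under that section.

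**SAP 8.5.** State that the study period for pregnancies runs from first dose through the Day 223 contact and includes those reported at that call. In Listing 15, flag those conceived within 3 months of the last dose. This keeps every pregnancy that the present wording may cover.

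**Cost.** One question in a call already planned, one SAP phrase and one flag in a listing. No visit, test or sample is added, and no dosing or contraception rule changes.

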8.9. Dose Escalation Criteria

The decision to advance to the next dose level will be based solely on the safety assessment. A dose level with no occurrence of stopping criteria will prompt moving to the next higher level. The Protocol Safety Review Team (PSRT) comprised of the Principal Investigator, the PATH Medical Officer, and the Independent Research Monitor will review blinded safety data for the recommendation to proceed with dose escalation.

8.10. Stopping Criteria

The study will use a dose-escalation design to evaluate increasing doses of Invaplex_{AR}-DETOX.

The PI, along with the PSRT, may determine a subject's local site reactions warrant discontinuation of subsequent vaccinations for that subject. If it is determined that a subject will not continue with future vaccine doses, they may remain enrolled in the study for follow-up.

If any of the following events occurs, administration of investigational product will be discontinued for the group until a thorough review of the event is undertaken by the investigators and the PSRT:

- The occurrence of one serious adverse event determined to be related to the investigational vaccine (definitely, probably, or possibly) at any time post-vaccination.
- Severe diarrhea, defined as six or more liquid stools within 24 hours of vaccination.
- A severe local rash, defined as one that makes the subject unable to perform normal daily activities and which is not attributable to another cause.
- Systemic rash, including but not limited to generalized urticarial, generalized petechiae, or erythema multiforme, occurring in two or more subjects in a group will result in stopping further vaccination in subject's group.
- One vaccine-related serious or unexpected AE evaluated by the principal investigator (PI), Independent Research Monitor, and sponsor and determined to be an unacceptable risk to the health and safety of other investigational product recipients.
- If a subject experiences grade 2 or greater hypotension in the 30 minutes following vaccination, they will not be eligible to receive subsequent vaccinations.

Further vaccination, in accordance with the protocol, may be resumed with the concurrence of the PRST, sponsor's representative, the PI, and the US Food and Drug Administration (FDA).

An interim analysis for each cohort will be prepared and reviewed to include all safety data through seven days after the third vaccination dose for each cohort. This report will be provided to the PSRT for their review to determine whether the study can continue to enroll for the next, dose-escalating cohort or whether the study should be stopped. In addition to the interim safety analyses, the PI, sponsor's representative along with the PSRT will stop the study until further review by the PSRT if any of the following criteria that are thought to be definitely, probably, or possibly related to the investigational vaccine are identified:

- One or more SAEs, including grade 4 adverse events or laboratory abnormalities.
- Two or more grade 3 adverse events or laboratory abnormalities of the same type.
- One or more grade 3 laboratory abnormalities.
- Two or more grade 2 laboratory abnormalities.

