8.12.1.2. Systemic Reactions

Any vaccine may be associated with a wide range of systemic reactions, such as fevers, constitutional symptoms (fatigue, malaise, appetite change), and gastrointestinal symptoms (diarrhea, abdominal pain) as well as others to include allergic reactions (bronchospasm, urticaria, anaphylaxis). The frequency and type of systemic symptoms will be assessed and analyzed with respect to study product.

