4.5.1. Adverse Events

4.5.1.1. Reactogenicity Events

Solicited AEs are pre-specified local and general (systemic) adverse events that are common and known to occur or are of particular interest following administration of the study vaccine. For this trial, solicited AEs will be assessed by study staff 30 minutes after each vaccination and then by study subjects daily for 7 days (day of vaccination and subsequent 7 days). Subjects are provided a diary card for recording the presence or absence and severity of solicited AEs.

Investigators will review diary cards with the subject and document positive findings on source documents or progress notes.

Solicited reactogenicity events include the following:

Local Reactions:

- Site pain, site tenderness, swelling, induration, site redness and pruritus.

Systemic Reactions:

- Fever, nausea, vomiting, abdominal pain, diarrhea (loose stools), appetite change, fatigue, headache, myalgias, arthralgias and malaise.

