8.3. Adverse Events

The primary objective of this study is safety of the Invaplex_{AR}-DETOX vaccination. All summaries of adverse events will be presented by vaccine dose (1 to 3) and overall, and by treatment group. Safety summaries and analyses will be presented for the Safety Population.

Local and general (systemic) solicited AEs, as well as lymph node assessments, are collected within 30 minutes of each vaccine dose and through 7 days following each dose (day of vaccination and subsequent 7 days). Lymph nodes are assessed as palpable or not palpable and for tenderness (yes/no). All other solicited events and symptoms are graded as 0 (normal), 1 (mild), 2 (moderate), 3 (severe), and 4 (potentially life-threatening). All general and local reactions are listed below.

Local Reactions:

- Site pain, site tenderness, swelling, induration, site redness and pruritus.

General Reactions:

- Fever, nausea, vomiting, abdominal pain, diarrhea (loose stools), appetite change, fatigue, headache, myalgias, arthralgias and malaise.

Adverse events will be summarized by MedDRA[®] system organ class (SOC), preferred term (PT), severity (mild, moderate, severe, potentially life-threatening) and whether related (definitely, probably or possibly) or not related (unrelated, unlikely) to study product. When calculating the incidence of adverse events (i.e., on a per subject basis), each subject will only be counted once per category. Per protocol, all adverse events occurring within 28 days of the third vaccination (Day 71) will be presented ([Table 18, Appendix A](#) and [Listing 10, Appendix C](#)). All events reported on the adverse event CRF will be included in the listing.

To assess safety, the number and percentage of subjects experiencing at least one AE, and the number and percentage of subjects experiencing each specific AE, categorized by body system, preferred term and product administered (for individual post-dose periods and for the entire study period) along with exact 95% CIs, will be tabulated. Overall summaries by study group include the number and percentage of subjects experiencing: (1) any adverse experience; (2) any Grade 2 or greater AE; (3) any AE judged related to study product; (4) any Grade 2 or greater AE judged related to study product; (5) Any SAE; (6) Any SAE related to IP.

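### Two systemic rashes pause a dose group, but generalized rash or hives is not a solicited event; one extra diary line would close a small gap

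*Protocol*

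**What the plan says.** Protocol 8.10 lists events after which administration is "discontinued for the group until a thorough review of the event is undertaken" by the investigators and the safety review team. One of them is "Systemic rash, including but not limited to generalized urticarial, generalized petechiae, or erythema multiforme, occurring in two or more subjects in a group". That bullet carries no grade and no relatedness condition, whereas the bullet on local rash requires a severe rash with no other cause. Protocol 8.9 moves the trial to the next dose level when no stopping criterion has occurred.

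On ascertainment, Protocol 8.6.1 states: "Solicited adverse event monitoring will survey and specifically inquire about symptoms listed in section 11.6.2". That list has 17 terms, and none is rash, urticaria, petechiae or erythema multiforme. The SAP carries the same 17 terms in 3.2.1.1, 4.5.1.1 and 8.3, as six local and eleven systemic. The systemic ones are: "Fever, nausea, vomiting, abdominal pain, diarrhea (loose stools), appetite change, fatigue, headache, myalgias, arthralgias and malaise". SAP 4.5.1.1 describes the diary in terms of that list: "Subjects are provided a diary card for recording the presence or absence and severity of solicited AEs".

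The event is foreseen. Protocol 8.12.1.2 names, beyond fever, constitutional and gastrointestinal symptoms, "others to include allergic reactions (bronchospasm, urticaria, anaphylaxis").

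**The concern.** The rule counts to two, so one unrecorded case can decide whether it is met. Because the bullet states no severity, a mild generalized rash appears to count. A mild, short-lived rash is also the kind most likely to go unmentioned if nobody asks about it by name.

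Two things depend on the count: the pause and review within the group, and whether the dose level can be described as free of stopping events when escalation is considered. This product has not been given to humans before, so the plan's own early-warning events should be asked about directly where that is easy to do.

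**Working it through.** **1. The plan's own figure.** Protocol 12.2 and SAP 5 give a 95% interval of 0 to 21% for no events in 16 subjects. The exact two-sided upper limit is 1 − 0.025^(1/16) = 0.206, so the figure reproduces. The plan gives no rash rate, no capture rate and no operating figure for the rash rule.

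**2. Trigger against solicited terms.** The nearest solicited terms are site redness, which is confined to the injection site, and pruritus, which the SAP classes as local. Pruritus may flag an itchy generalized rash, but petechiae need not itch. No solicited term asks for a generalized rash.

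**3. Where a rash could be missed.** Protocol 8.5.1: "Subjects will return approximately 24 hours and 7 days after vaccination for follow-up". Each visit includes an examination. With the second examination on post-dose day e, the days with no visit run from day 2 to day e − 1, which is e − 2 days. Taking vaccination on its nominal day and the windows in Protocol Table 8:

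| Dose | Follow-up visit | e | Days between visits |
|---|---|---|---|
| any, nominal | 7 days post-dose | 7 | 5 (days 2 to 6) |
| 1 | Day 8 ± 1 | 6 to 8 | 4 to 6 |
| 2 | Day 29 ± 2 | 5 to 9 | 3 to 7 |
| 3 | Day 50 ± 3 | 4 to 10 | 2 to 8 |

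**4. Illustration under assumed rates.** Let p be the true proportion of vaccinees with systemic rash and c the share of those rashes recorded. Both are assumptions. With n = 16 and q = p × c,

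P(two or more recorded) = 1 − (1 − q)^16 − 16q(1 − q)^15.

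For p = 5% and c = 1 this is 1 − 0.440 − 0.371 = 0.189.

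| True rate p | c = 100% | 90% | 75% | 50% |
|---|---|---|---|---|
| 1% | 1.1% | 0.9% | 0.6% | 0.3% |
| 2% | 4.0% | 3.3% | 2.3% | 1.1% |
| 5% | 18.9% | 16.0% | 11.9% | 5.9% |
| 10% | 48.5% | 42.9% | 34.0% | 18.9% |

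Only rashes confined to the days between visits are at risk. If f is the share confined there and u the share of those never reported, then c = 1 − f × u. Taking f = u = 0.5 gives c = 0.75, so the 50% column is pessimistic.

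**The case against.** The strongest reply is that an event can be collected without being solicited. Protocol 11.5.1 records unsolicited symptoms, 11.5.3 puts a focused examination at every visit, 11.8.1 has adverse events assessed at every visit, and 8.5.1 reminds subjects to call with problems. SAP 4.5.1.1 has investigators go through the diary card with the subject. The diary may also be wider than the solicited list: under Protocol 8.5 subjects are "given symptom diaries to record local and systemic reactions for 7 days post vaccination for each dose", and SAP 3.3.1.2 allows unsolicited events to be found from diary cards. The safety review team sees unsolicited events too (Protocol 11.4.1, SAP 6.6). All of this stands, and it is why the gap is small.

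A reader might infer that rash is an oversight because diarrhea, another halting symptom, is solicited. The documents do not support that. Severe local rash also halts a group and is not solicited by name, and nothing requires stopping events to be solicited. Protocol 11.6.2 ties solicited events to the Investigator's Brochure, which is not among the documents, so it cannot be said that rash was wrongly left off.

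It is also fair that silence on severity is not a statement that mild rash counts. The examples in the bullet are generalized urticaria, generalized petechiae and erythema multiforme. But the adjacent local-rash bullet does set a severity condition, so the natural reading of the systemic bullet is that it has none.

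What survives is narrow: a transient mild generalized rash between visits is recorded only if general enquiry draws it out, the subject volunteers it, or the diary has an open entry. The diary form is not available to settle the last of these.

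**Conclusion.** The point holds as a low-cost improvement. A count-of-two rule with unspecified severity depends on an event that no solicited list names, and the ordinary safeguards leave a short between-visit window for mild cases.

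A reader might infer that the rule is disabled, or that tens of percentage points of sensitivity are lost. The documents support neither. The largest loss in the table, from 48.5% to 18.9%, needs both a 10% rash rate and 50% capture. Going from full to 50% capture costs 0.8 percentage points at a 1% rate and 2.9 at a 2% rate. All of these figures rest on assumed rash and capture rates and on independence between subjects. The consequence of the trigger is a pause for review, not termination. No sample size, alpha or confidence interval in the plan is affected.

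**What to change.** Add one line, 'generalized rash/hives' (yes/no, with severity), to Protocol 11.6.2, the diary card and the solicited lists in SAP 3.2.1.1, 4.5.1.1 and 8.3. If the diary already has such a line, only the lists need to be aligned. If mild rash was never meant to halt a group, Protocol 8.10 should state the grade that counts.

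The cost is a minor amendment, one diary line and matching SAP edits. The downside is slightly more recorded mild rash in all groups, placebo included, and a somewhat higher chance of a pause. A pause is not free, since Protocol 8.10 requires agreement from the safety review team, the sponsor, the investigator and the FDA before vaccination resumes.
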